### Target Sample Size

Assuming 46% of the Control patients and 50.5% of the Envi™-SR patients have an mRS score

$\leq 2$  at 90 days, 270 total subjects (ITT) will be required.

### Maximum Sample Size

If the gap narrows between the 2 randomized groups to 49.5% (Control) and 50.5% (Envi™-SR), 426 total patients (ITT) will be required (type 1 error rate of 2.5%, power of 80%). A loss to follow-up rate of 5% or less is expected. Missing data will be imputed as described in section 8.2.2. As multiple imputation could dampen the signal from the subject data that is imputed, an additional 5% of subjects may be added to compensate for any potential impact, leading to a total sample size of 448 subjects (ITT).

All estimates are performed based on the ITT population. However, all enrolled subjects (i.e., consented), including enrolled screen failures, will count toward the maximum sample size of 560 patients. The rate of enrolled screen failures is not expected to exceed 25%. Therefore, the maximum sample size for enrollment will be the ITT maximum sample size plus 25%, or 560 patients.

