### Additional Estimates

Estimates were also prepared under situations where the gap between arms remains consistent but both proportions shift to account for effects such as Additional Therapy methods. Sample sizes remain sufficient under these situations, see the SAP for additional detail.

Estimates were also prepared for the secondary endpoints. For the primary safety endpoint (sICH within 24 hours (-8/+12 hours) after the study procedure), the incidence of sICH is not expected to exceed 4% in either arm of the study. The total sample size required for 80% power, a type 1 error rate of 2.5%, and a non-inferiority margin of 7% is 318 patients.

For the proportion of patients with eTICI 2b50 or greater flow (single pass and after a maximum of 3 passes, the incidence is expected to be ~74% in both arms of the study. The total sample size required for 80% power, a type 1 error rate of 2.5%, and a non-inferiority margin of 12.2% is 408 patients.

Ninety days following the index stroke, mortality is not expected to be exceeded ~13.8% in both arms of the study. The total sample size required for 80% power, a type 1 error rate of 2.5%, and a non-inferiority margin of 10% is 390 patients.

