**Table 8.1: Unadjusted Mean and 95% Confidence Limits on the Literature Rates**

Study	N	X	Y c	VAR a	W c	W c Y c	W c 
-------	---	---	----------------	------------------	----------------	-------------------------------	-----------------------------

SWIFT PRIME	98	59	0.6020	0.0024448	409.036071	246.25641	167310.508
ESCAPE	120	64	0.5333	0.0020741	482.142857	257.142857	232461.735
REVASCAT	103	45	0.4369	0.0023885	418.669349	182.913793	175284.024
EXTEND IA	35	25	0.7143	0.0058309	171.5	122.5	29412.25
MRCLEAN	233	76	0.3262	0.0009433	1060.11876	345.789809	1123851.78
				SUM	1154.60287	2541.46703	1728320.29
					$\bar{Y}$	LCL	UCL
				C=5	0.4543	0.4154	0.4932
a The VAR term in the table is actually the standard error of the $Y_c$ .							

In Table 8.2, the test of heterogeneity is computed and the adjustment if  $Q > C-1$ .

Table 8.2: Adjusted Mean and 95% Confidence Limits on the Literature Rates							
Study	$Y_c$	$\bar{Y}$	$Y_c - \bar{Y}$	$(Y_c - \bar{Y})^2$	$W_c (Y_c - \bar{Y})^2$	$W_c^*$	$W_c^* Y_c^*$
SWIFT PRIME	0.6020	0.4543	0.1477	0.02182568	8.9275	44.7338	26.9316
ESCAPE	0.5333	0.4543	0.0790	0.00624537	3.0112	45.4881	24.2603
REVASCAT	0.4369	0.4543	-0.0174	0.00030319	0.1269	44.8467	19.5932
EXTEND IA	0.7143	0.4543	0.2600	0.06758963	11.5916	38.8492	27.7494
MRCLEAN	0.3262	0.4543	-0.1281	0.01641612	17.4030	47.9548	15.6419
				SUM $Q=$	41.0602	221.8726	114.1764
$\bar{W}=$	508.29341						
$S_W^2=$	109127.34			$D_1=$	0		
U=	1861.4188			$D_2=$	0.01990968		
				$\bar{Y}^*$	$SE(\bar{Y}^*)$	LCL	UCL
				0.5146	0.0671	0.3830	0.6462

Since  $Q > C-1$ , an adjustment was made to the mean success rate and the between study standard error has increased to 0.0671. This demonstrates that the upper and lower limits are  $0.5146 \pm 0.1315$  (1.96-0.0671). The variability between and within the five (5) studies is 0.13 (13%) and a margin of equivalence that size or smaller would be appropriate. The non-inferiority margin for this study will be set at -12.5%.

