### 8.3.2. Analysis of the Secondary and Tertiary Endpoints

If non-inferiority is achieved based on the primary endpoint, a hierarchical step-down approach will be used to test the secondary endpoints in rank order. The following secondary effectiveness endpoints will be compared between the two treatment arms:

1. The first secondary effectiveness endpoint will be an assessment of the mRS shift from baseline at 90 days ( $\pm 15$  days) following the study index procedure. The Cochran–Mantel–

Haenszel test will be used to derive the 95% confidence intervals for the overall odds ratio. If the 95% confidence intervals for the overall odds ratio does not contain 1, the conclusion will be that the mRS shift is not proportional between the 2 devices. This is a 2-sided evaluation of the odds ratio.

2. The second secondary effectiveness endpoint will be an assessment of the proportion of patients who achieve reperfusion measured using the expanded Thrombolysis in Cerebrovascular Infarction index (eTICI). Successful achievement of the endpoint is defined as achieving an eTICI score of 2b50 or greater [eTICI 2b50-3] in the target vessel following three or less passes of the randomized device (as adjudicated by Core Lab). If the lower bound of the 1-sided 97.5% confidence interval of the difference (Envi™-SR minus Control) in the proportion of patients with eTICI 2b50 or greater flow in the target vessel post-procedure is numerically greater than -12.1%, Envi™-SR will be considered non-inferior to Control. This is a 1-sided evaluation to establish non-inferiority.
3. The third secondary effectiveness endpoint will be an assessment of the proportion of patients in whom a successful First Pass Effect is achieved. Successful achievement of the endpoint is defined as achieving an eTICI First Pass Effect (FPE) defined as eTICI 2c-3 after a single pass (as adjudicated by Core Lab). If the lower bound of the 1-sided 97.5% confidence interval of the difference (Envi™-SR minus Control) in the proportion of patients with eTICI 2c or greater flow in the target vessel post- first pass is numerically greater than -12.1%, Envi™-SR will be considered non-inferior to Control. This is a 1-sided evaluation to establish non-inferiority.

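### The 560-consent cap yields 420 ITT subjects, not 448, at the plan's own 25% screen-failure ceiling, and the 270 target is below the plan's own 318 for primary safety

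*Combined protocol and SAP*

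**What the plan says.** **Enrollment cap.** Section 8.2 (Maximum Sample Size) derives 426 ITT subjects and adds 5% for missing data, reaching 448. It counts everyone consented, screen failures included, toward 560. Section 5.1.1.1 confirms that consented screen failures use up the allowed enrollment. On the failure rate, 8.2 says "The rate of enrolled screen failures is not expected to exceed 25" per cent, and it concludes that "the maximum sample size for enrollment will be the ITT maximum sample size plus 25%, or 560 patients". Section 6.3 gives 448 as the study maximum without saying which population is meant.

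**Target size and primary safety.** The target rests on primary effectiveness: "Assuming 46% of the Control patients and 50.5% of the Envi™-SR patients have an mRS score" of 2 or less, so "270 total subjects (ITT) will be required". The Synopsis (Statistics) makes sICH a primary safety endpoint with a 7% margin and has both primaries evaluated at the same time. Section 8.2 (Additional Estimates) sizes that endpoint at 4% sICH and 80% power: the total at a one-sided 2.5% level "and a non-inferiority margin of 7% is 318 patients". The figure appears in a paragraph introduced as covering the secondary endpoints.

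**eTICI margin.** The same subsection sizes eTICI 2b50 or better at 74% in both arms, with 80% power "and a non-inferiority margin of 12.2% is 408 patients". Section 8.3.2 tests it by whether the lower bound "is numerically greater than -12.1%, Envi™-SR will be considered non-inferior to Control".

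**The concern.** Adding 25% to the ITT number does not allow for a 25% failure rate among those consented; that needs division by 0.75. As written, the cap can be reached before the planned maximum ITT size.

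The two primary endpoints also have different stated size requirements, and the target meets only the smaller one. The interim in the Synopsis and Section 8.1 re-sizes on conditional power, and neither place mentions the safety requirement. If effectiveness looks good at the interim, the trial continues to 270, which is where primary safety has less than 80% power on the plan's own inputs. A reader of 8.2 is told neither fact.

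**Working it through.** **1. Reproduce the plan's sizes.** Inputs from 8.2: 1:1 allocation, one-sided 2.5%, 80% power, and the stated rates and margins (for the primary, "The non-inferiority margin for this study will be set at -12.5" per cent). The Farrington–Manning score formula per arm is

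n = [(1.960·s0 + 0.8416·s1) / (pT − pC + margin)]²

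where s1² = pT(1−pT) + pC(1−pC), and s0² is the same sum at the rates fitted under the null. Outcomes are coded so that higher is better.

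| Endpoint | Rates (Envi-SR / Control) | Margin | Total before rounding | Total, equal arms | Plan |
|---|---|---|---|---|---|
| mRS ≤2, target | 50.5% / 46% | 12.5% | 268.1 | 270 | 270 |
| mRS ≤2, maximum | 50.5% / 49.5% | 12.5% | 425.9 | 426 | 426 |
| sICH-free | 96% / 96% | 7% | 317.9 | 318 | 318 |
| eTICI 2b50+ | 74% / 74% | 12.2% | 406.5 | 408 | 408 |
| 90-day survival | 86.2% / 86.2% | 10% | 389.4 | 390 | 390 |

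All five agree. The unpooled (Wald) formula gives 272, 432, 248, 406 and 374, so the plan's sizing evidently used the score method.

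**2. Enrollment cap.**
- Plan: 426 × 1.05 = 447.3, taken as 448; 448 × 1.25 = 560.
- ITT at 25% failures: 560 × (1 − 0.25) = 420. Shortfall: 448 − 420 = 28; 426 − 420 = 6.
- Failure rate at which 560 still gives 448: 1 − 448/560 = 20%. For 426: 1 − 426/560 = 23.9%.
- Consents needed for 448 at 25%: 448/0.75 = 597.3, so 598.

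**3. Effect on primary effectiveness power.** Power = Φ{[√n·(pT − pC + margin) − 1.960·s0]/s1}. At 50.5%/49.5%, s0 = 0.7016 and s1 = 0.7071. For 420 (n = 210): (14.491 × 0.135 − 1.375)/0.7071 = 0.822, so power is 79.4%. The same formula gives 80.0% at 426 and 81.9% at 448. If 5% of the 420 contributed nothing (420 × 0.95 = 399), it gives 77.4%.

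**4. Primary safety at 270.** At 4% sICH, s0 = 0.3313 and s1 = 0.2771.
- Size: [(0.6493 + 0.2332)/0.07]² = 159.0 per arm, total 318, as stated.
- Power at 270 (n = 135): (11.619 × 0.07 − 0.6493)/0.2771 = 0.592, so 72.3%.
- By sICH rate, power at 270 is 72.3% at 4%, 76.0% at 3.5%, 79.9% at 3% and 88.8% at 2%.
- By interval method at 4%, exact enumeration at 270 gives about 74% (score), 75% (continuity-corrected) and 84% (Wald).
- At 420 to 448 ITT, the score formula gives about 91 to 92%.

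**5. Both primaries at 270.** Effectiveness power is 80.3%. With independence and 4% sICH, 0.803 × 0.723 = 58%.

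**6. eTICI.** At 12.1% the total is 413.3, so 414 against 408 at 12.2%. Power at 270 is 61.9% against 62.7%.

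**The case against.** Much of the opposing case stands.

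- **25% and 4% are ceilings.** The 420 is therefore the worst case the plan allows for, and 72% applies at the highest sICH rate expected.
- **The cap costs little power.** The 5% addition is optional in the text, missing outcomes are to be imputed, and 560 still delivers 426 up to 23.9% failures.
- **The rate could be read as failures per ITT subject.** Then 112/448 = 25% and 560 is right. But 5.1.1 defines enrolled as consented, and 8.2 speaks of enrolled screen failures, so the consented denominator is the natural one.
- **318 is disclosed.** A reader might infer that the plan promises 80% safety power at 270. It makes no such claim; the gap is that 318 and 270 are never reconciled.
- **The safety interval method is not named.** The Synopsis gives only a one-sided 97.5% interval, and a Wald interval would bring power at 270 above 80%.

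Three stronger readings are tempting. The first is that none of the stated sizes is delivered; that is untrue of 270, which is attainable and correct for primary effectiveness. The second is that overall power is only 58%. No passage makes success depend on both primaries, and the secondary hierarchy opens on effectiveness alone. The third is that safety size is ignored at the interim. The supplied text only fails to mention it: the DMC receives all adverse events, its check against planning estimates is left to its Charter, and 8.2 refers sizing detail to the SAP. Neither the Charter nor separate SAP text could be checked.

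**Conclusion.** The concern holds in limited form and should be fixed. The step from 448 to 560 is an arithmetic error: at 25% failures among those consented, the cap gives 420 ITT, and it gives 448 only at 20% or fewer. The practical loss is the missing-data allowance and, against the planned 448, 2.5 percentage points of primary effectiveness power (81.9 − 79.4).

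The second part matters more if the trial ends at 270. Primary safety then has about 72% power at 4% sICH on the score method, and 80% only if sICH is about 3% or lower or a less conservative interval is used. It has little force if the trial is enlarged to 420 or more. The mismatch in eTICI margin is a minor inconsistency in secondary endpoints. None of these points affects the type I error rate of the primary effectiveness test.

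**What to change.** Restate the figures in 8.2, and in the SAP where they recur:

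1. Say that 560 consents support 448 ITT subjects only if screen failures are 20% or fewer of those consented, and 420 at 25%. Label the 448 in 6.3 as ITT.
2. Move the sICH estimate out of the secondary-endpoint paragraph and present it as a primary endpoint. Give its power at 270, with the dependence on sICH rate and interval method, and say that 80% is reached from 318 at 4%. Name the interval method.
3. If joint power is quoted (about 58% at 4% sICH under independence), label it as the chance of meeting both primary criteria.
4. Use one eTICI margin in 8.2 and 8.3.2 with its matching size: 12.1% with 414, or 12.2% with 408.

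The cost is text changes and figures that look slightly less favourable. No extra patients are needed. Raising the cap to 598 would also close the gap but would allow 38 more consents (598 − 560), and the small power loss does not require it.

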### Additional Estimates

Estimates were also prepared under situations where the gap between arms remains consistent but both proportions shift to account for effects such as Additional Therapy methods. Sample sizes remain sufficient under these situations, see the SAP for additional detail.

Estimates were also prepared for the secondary endpoints. For the primary safety endpoint (sICH within 24 hours (-8/+12 hours) after the study procedure), the incidence of sICH is not expected to exceed 4% in either arm of the study. The total sample size required for 80% power, a type 1 error rate of 2.5%, and a non-inferiority margin of 7% is 318 patients.

For the proportion of patients with eTICI 2b50 or greater flow (single pass and after a maximum of 3 passes, the incidence is expected to be ~74% in both arms of the study. The total sample size required for 80% power, a type 1 error rate of 2.5%, and a non-inferiority margin of 12.2% is 408 patients.

Ninety days following the index stroke, mortality is not expected to be exceeded ~13.8% in both arms of the study. The total sample size required for 80% power, a type 1 error rate of 2.5%, and a non-inferiority margin of 10% is 390 patients.

### 8.2.1. Justification for the Non-Inferiority Margin for the Primary Effectiveness Endpoint

The inverse variance weighting method developed by Fleiss (1993) and later provided in Fleiss et al. (2003) was used to establish the non-inferiority margin. There are five (5) randomized trials demonstrating the benefit of revascularization after ischemic stroke that form the basis of such analyses. Goyal et al. (2015) presented the results of the ESCAPE trial, Berkhemer et al. (2015) presented the MRCLEAN trial, Jovin et al. (2015) presented the results of the REVASCAT trial, Campbell et al. (2015) presented the results of the EXTEND IA trial, and Saver et al. (2015) presented the results of the SWIFT PRIME trial. The five studies were combined by this method in the tables below. The first table provides the estimate unadjusted for heterogeneity and the second table adjusts the estimate for heterogeneity based on the value of Q. Only the test arm of the five trials are provided below with success being defined as having a 90-day modified Rankin Score of 0 to 2.

**Table 8.1: Unadjusted Mean and 95% Confidence Limits on the Literature Rates**

Study	N	X	Y c	VAR a	W c	W c Y c	W c 
-------	---	---	----------------	------------------	----------------	-------------------------------	-----------------------------

SWIFT PRIME	98	59	0.6020	0.0024448	409.036071	246.25641	167310.508
ESCAPE	120	64	0.5333	0.0020741	482.142857	257.142857	232461.735
REVASCAT	103	45	0.4369	0.0023885	418.669349	182.913793	175284.024
EXTEND IA	35	25	0.7143	0.0058309	171.5	122.5	29412.25
MRCLEAN	233	76	0.3262	0.0009433	1060.11876	345.789809	1123851.78
				SUM	1154.60287	2541.46703	1728320.29
					$\bar{Y}$	LCL	UCL
				C=5	0.4543	0.4154	0.4932
a The VAR term in the table is actually the standard error of the $Y_c$ .							

In Table 8.2, the test of heterogeneity is computed and the adjustment if  $Q > C-1$ .

Table 8.2: Adjusted Mean and 95% Confidence Limits on the Literature Rates							
Study	$Y_c$	$\bar{Y}$	$Y_c - \bar{Y}$	$(Y_c - \bar{Y})^2$	$W_c (Y_c - \bar{Y})^2$	$W_c^*$	$W_c^* Y_c^*$
SWIFT PRIME	0.6020	0.4543	0.1477	0.02182568	8.9275	44.7338	26.9316
ESCAPE	0.5333	0.4543	0.0790	0.00624537	3.0112	45.4881	24.2603
REVASCAT	0.4369	0.4543	-0.0174	0.00030319	0.1269	44.8467	19.5932
EXTEND IA	0.7143	0.4543	0.2600	0.06758963	11.5916	38.8492	27.7494
MRCLEAN	0.3262	0.4543	-0.1281	0.01641612	17.4030	47.9548	15.6419
				SUM $Q=$	41.0602	221.8726	114.1764
$\bar{W}=$	508.29341						
$S_W^2=$	109127.34			$D_1=$	0		
U=	1861.4188			$D_2=$	0.01990968		
				$\bar{Y}^*$	$SE(\bar{Y}^*)$	LCL	UCL
				0.5146	0.0671	0.3830	0.6462

Since  $Q > C-1$ , an adjustment was made to the mean success rate and the between study standard error has increased to 0.0671. This demonstrates that the upper and lower limits are  $0.5146 \pm 0.1315$  (1.96-0.0671). The variability between and within the five (5) studies is 0.13 (13%) and a margin of equivalence that size or smaller would be appropriate. The non-inferiority margin for this study will be set at -12.5%.

### 8.2.2. Missing and Censored Data

Missing data, which in this instance is defined as data that was not entered into the EDC system for analysis, may have an impact upon the interpretation of the trial data.

The primary presentation of the results for the primary and secondary endpoints using the ITT population will be based on the observed data with multiple imputation for missing endpoint data using SAS PROC MI. This procedure uses an iterative modeling approach to generate estimates for patients who withdraw prematurely, or the data is just not recorded, incorporating

multivariate imputation by fully conditional specification (FCS) methods. The discriminant function method will be used for classification variables. With the function method of classification, the missing values will be imputed sequentially in the following order:

- Age: ( $\geq 67$  and  $< 67$ )
- Site of occlusion: ICA, MCA M1, MCA M2
- Baseline/Enrollment NIHSS score ( $< 17$  and  $\geq 17$ )
- Prior IV t-PA usage (Yes / No)
- Time to symptom onset ( $\geq 6$  hours and  $< 6$  hours)
- Baseline ASPECTS (6-7 and 8-10)

Each missing score will be imputed ten times to generate ten imputed complete datasets based on the Markov Chain Monte Carlo (MCMC) method with age, occlusion site, NIHSS score ( $< 17$  /  $\geq 17$ ), baseline ASPECTS (6-7 / 8-10), prior IV t-PA usage (yes / no), and time to symptom onset ( $\geq 4$  hours /  $< 4$  hours) entered into the model following this sequential order. The imputed score will be rounded to the first decimal point for continuous variables. Proc MIANALYZE will be used to combine the imputed datasets to render an analysis of the binary outcomes for the results for the primary effectiveness and safety endpoints and the applicable 4 secondary endpoints. The relevant secondary endpoint analysis will follow the method outlined to calculate the odds ratio with the imputed dataset.

Additional sensitivity analyses will also be conducted as a secondary examination of the primary analysis using the last observation recorded following the procedure observation carried forward. A tipping point analysis will also be conducted.

If a patient did not have solicited adverse events of special interest [incidence by type of event] prior to withdrawing prematurely from the study, the patient will be considered as not having experienced the event.

Additional details for addressing partial and completely missing dates are addressed in the Statistical Analysis Plan.

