#### 3.2. Secondary Effectiveness Endpoints

The following secondary effectiveness endpoints will be described and compared between the two treatment arms:

1. The first secondary effectiveness endpoint will be an assessment of the mRS shift from baseline at 90 days ( $\pm$  15 days) following the study index procedure.
2. The second secondary effectiveness endpoint will be an assessment of the proportion of patients who achieve reperfusion measured using the expanded Thrombolysis in Cerebrovascular Infarction index (eTICI). Successful achievement of the endpoint is defined as achieving an eTICI score of 2b50 or greater [eTICI 2b50-3] in the target vessel following three or less passes of the randomized device (as adjudicated by Core Lab).
3. The third secondary effectiveness endpoint will be an assessment of the proportion of patients who achieve a successful First Pass Effect. Successful achievement of the endpoint is defined as achieving an eTICI First Pass Effect (FPE) defined as eTICI 2c-3 after a single pass (as adjudicated by Core Lab).
4. The fourth secondary effectiveness endpoint will be an assessment of the proportion of patients who achieve a successful Modified First Pass Effect. Successful achievement of the endpoint is defined as achieving an eTICI Modified First Pass Effect (mFPE) defined as eTICI 2b50-3 after a single pass (as adjudicated by Core Lab).
5. The fifth secondary effectiveness endpoint will be an assessment of the proportion of subjects with Early Response defined as a NIHSS drop of  $\geq 10$  points from baseline or NIHSS score 0 or 1 at seven (7) days (-2/+3 days) or discharge, whichever is sooner.

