### 4.1. Measurement Scales

The following measurement scales will be used in the NV-001 Study:

- *mRS* – The modified Rankin Scale (mRS) is a commonly used scale for measuring the degree of disability or dependence in the daily activities of people who have suffered a stroke or other causes of neurological disability.
- *NIHSS* - The National Institutes of Health Stroke Scale, or NIH Stroke Scale (NIHSS) is a tool used by healthcare providers to objectively quantify the impairment caused by a stroke. The NIHSS is composed of 11 items, each of which scores a specific ability between a 0 and 4. For each item, a score of 0 typically indicates normal function in that specific ability, while a higher score is indicative of some level of impairment. The individual scores from each item are summed in order to calculate a patient's total NIHSS score. The maximum possible score is 42, with the minimum score being a 0.
- *eTICI* Expanded Thrombolysis in Cerebral Infarction score. The thrombolysis in cerebral infarction (TICI) grading system is a tool for categorizing the degree of reperfusion during or after ischemic stroke. In neurointerventional radiology it is commonly used for patients post endovascular revascularization. The eTICI is a 7-point compilation of TICI grades that reflects all previously reported thresholds used to define reperfusion after endovascular stroke therapy. eTICI provides granularity in distinguishing the extent of reperfusion that is clinically meaningful.
- *Heidelberg Bleeding Classification* – The Heidelberg Bleeding Classification will be used to categorize intracranial hemorrhage into sICH or aICH based on both a pure

radiological classification scheme and a combined radiological-symptomatic classification scheme. The Heidelberg Bleeding Classification was created to classify bleeding events after reperfusion therapy for reporting in AIS device trials. It provides a framework for classification of intracranial hemorrhage into classes, including hemorrhagic infarction (HI1, HI2), parenchymatous hematoma (PH1, PH2, rPH), intraventricular hemorrhage (IVH), subarachnoid hemorrhage (SAH), and subdural hemorrhage (SDH); and for classification of sICH vs. aICH.

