### **5.3. Subject Withdrawals**

Participation in this IDE Study is voluntary, and the subject may withdraw at any time. All ITT subjects will be included in data analysis, unless they withdraw permission for their data to be used. The Sponsor will retain and continue to use any data collected prior to the withdrawal of informed consent, unless specified by the subject or their LAR.

In the event the subject chooses to withdraw, he/she will be instructed to contact the Investigator immediately. Withdrawal from the investigation will not affect the subject's follow-up care. The subject will be informed of any significant information regarding new findings that may develop during the course of the research study that may relate to his or her willingness to continue participation as a study subject.

Subjects will participate in their routine follow-up and allow this data to be gathered or their participation in the study will be prematurely terminated. If their participation is terminated, any of their data which has been already gathered will continue to be included. The completion of a subject's participation in the study or early departure from the study must be fully documented in the subject's study progress notes.

Subjects will be considered exited (i.e., discontinued) from the study if any of the following occur:

1. If, during the conduct of the study, a subject dies, all available information should be obtained, and an appointed NeuroVasc Technologies representative/ study monitor should be notified no more than 24 hours from study staff becoming aware of the event.
  - a. If a subject's death occurs while in the hospital, submit a copy of the physician's death summary report. If an autopsy is performed, submit a copy of the autopsy report, as well. If a subject's death occurs outside of the study site, obtain all information related to the death and submit the investigator's summary of the events associated with the death.
2. Subject voluntarily withdraws from the study. A subject may withdraw consent from study participation at any time.
3. Subject does not meet inclusion / exclusion criteria after consent but prior to randomization (enrolled screen failure). The subject will be followed for a minimum of 48 hours or until discharge, whichever is earlier, and exited from the study.
4. Subject withdrawn from the study by the investigator. An investigator may withdraw an enrolled subject from the study for the following reasons:

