4. The fourth secondary effectiveness endpoint will be an assessment of the proportion of patients in whom a successful Modified First Pass Effect is achieved. Successful achievement of the endpoint is defined as achieving an eTICI Modified First Pass Effect (mFPE) defined as eTICI 2b50-3 after a single pass (as adjudicated by Core Lab). If the lower bound of the 1-sided 97.5% confidence interval of the difference (Envi™-SR minus Control) in the proportion of patients with eTICI 2b50 or greater flow in the target vessel post- first pass is numerically greater than -12.1%, Envi™-SR will be considered non-inferior to Control. This is a 1-sided evaluation to establish non-inferiority.
5. The fifth secondary effectiveness endpoint will be an assessment of the proportion of subjects with Early Response defined as a NIHSS drop of  $\geq 10$  points from baseline or NIHSS score 0 or 1 at seven (7) days (-2/+3 days) or discharge, whichever is sooner. If the probability value from the 2-tailed Fisher's exact test is  $< 0.05$  and the proportion of patients with an NIHSS of 0 or 1, or improvement in the NIHSS of 10 points or more from the baseline (pre-procedure) score is greater in the Envi™-SR treatment arm compared to the control arm, the null hypothesis will be rejected and Envi™-SR will be considered superior to Control. This is a 2-sided evaluation of the proportions.

The details for analyzing the individual tertiary endpoints are presented in the SAP.

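### Applied literally, the missing-data rule imputes Early Response for subjects who die before the day-7/discharge NIHSS, and counts some of them as responders

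*Combined protocol and SAP*

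**What the plan says.** **Endpoint.** Early Response, the fifth secondary effectiveness endpoint, is a fall of at least 10 NIHSS points from baseline "or NIHSS score 0 or 1 at seven (7) days (-2/+3 days) or discharge, whichever is sooner" (Section 3.2). No part of the definition refers to death. Section 4.1 gives the range of the scale: "The maximum possible score is 42, with the minimum score being a 0". By contrast, the mRS table in Appendix A has a category for death, score 6.

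**Test.** Section 8.3.2, item 5, names a two-tailed Fisher's exact test at 0.05. If it is significant and the Envi-SR proportion is the higher, "the null hypothesis will be rejected and Envi™-SR will be considered superior to Control". The item ends: "This is a 2-sided evaluation of the proportions".

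**Missing data.** Section 8.2.2 begins with a broad definition: "Missing data, which in this instance is defined as data that was not entered into the EDC system for analysis". It applies multiple imputation in the ITT population to the primary and secondary endpoints, through a procedure that "uses an iterative modeling approach to generate estimates for patients who withdraw prematurely, or the data is just not recorded". The imputed datasets are combined for the binary outcomes, including four secondary endpoints. Endpoints 2 to 5 are the four binary ones, so Early Response is among them. The listed model variables are age, occlusion site, NIHSS category, ASPECTS category, prior IV t-PA and time to onset. Treatment arm, 24-hour NIHSS and vital status are not listed.

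**Status of a death.** Section 5.3 states: "Subjects will be considered exited (i.e., discontinued) from the study if any of the following occur". Death is the first item in the list that follows.

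**The concern.** A subject who dies on day 3 has no day-7/discharge NIHSS to enter. Under the Section 8.2.2 definition that value is missing, and the stated remedy is to draw it from a model of baseline factors. The model cannot tell this subject from a survivor with the same baseline profile, so the subject becomes a responder about as often as such a survivor does.

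Death is an outcome of the stroke or its treatment. It is not an unobserved NIHSS. Scoring some deaths as early neurological recovery inflates the response rate in each arm. It also distorts the comparison if one arm has more early deaths, on an endpoint that can support a statement of superiority.

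**Working it through.** **1. Arm size.** The documents give no expected rate, power or sample size for Early Response, so the plan supplies only the number of subjects. The target of 270 can be reproduced with rates of 46% and 50.5%, a margin of 12.5 points, one-sided 2.5% and 80% power (the error rate and power are stated with the maximum sample size):

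n per arm = (1.960 + 0.842)² × (0.46×0.54 + 0.505×0.495) / (0.045 + 0.125)² = 7.85 × 0.4984 / 0.0289 ≈ 135.4, so 136 per arm or 272 in total, against 270 stated. I use 135 per arm.

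**2. Deaths that could be imputed.** Appendix C gives 9.7% as the upper limit reported for death at 0-7 days: 135 × 0.097 = 13.1 per arm. This is an upper bound. It is the highest figure reported across the trials listed. In addition, the NIHSS is taken at day 7 or at discharge if sooner, so some subjects who die within seven days will already have a discharge value.

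**3. Deaths scored as responders.** Let p be the imputed probability of response (assumed, since the documents give none).

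| p | 13.1 × p |
|---|---|
| 30% | 3.9 |
| 45% | 5.9 |
| 60% | 7.9 |

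**4. Effect on the difference between arms.** Compared with scoring death as failure, the added difference is (d₁ − d₂) × p, where d₁ and d₂ are the early death rates. The comparator rate of 5% is an assumption.

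| p | (0.097 − 0.05) × p |
|---|---|
| 30% | +1.4 points |
| 45% | +2.1 points |
| 60% | +2.8 points |

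If d₁ = d₂ the added difference is zero.

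**5. Worked case with counts.** Assume 61 true responders of 135 in each arm (45.2%) and 13 versus 4 early deaths (9.7% versus an assumed 3%, a wider gap than in step 4). The pooled survivor rate is 122 / (270 − 17) = 0.482. Imputation adds 13 × 0.482 = 6.3 and 4 × 0.482 = 1.9 responders, giving 67.3/135 = 49.8% and 62.9/135 = 46.6%. The difference is +3.2 points where the true difference is zero. With 13 deaths in each arm, both rates become 50.0% and the difference stays at zero.

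**6. Effect on the test in that wider case.** A simulation used 4,000 runs per setting, ten imputations, Rubin's rules and a Wald test. The Wald test is a stand-in, because the plan does not say how Fisher p-values are pooled over imputations. At 9.7% versus 3% deaths, with equal response of 30%, 45% and 60% when death counts as failure, false superiority for the arm with more deaths was about 4%, 6% and 10% at 135 per arm (nominal 2.5%). At 224 per arm it was about 5%, 9% and 14%. With death scored as failure it stayed at 2.3-2.8%.

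**The case against.** **The plan never says that deaths are imputed.** Section 8.2.2 speaks of premature withdrawal, Section 8.3.1 speaks of loss to follow-up, and Section 5.3 lists death, voluntary withdrawal and loss to follow-up as separate items. This stands in part: the reading rests on a default rule, and no sentence names death. But the default is wide. It takes in anything not entered in the EDC system, and Section 5.3 counts death as discontinuation. Section 8.2.2 writes a specific rule for adverse events after withdrawal but none for death on the NIHSS. The worst-score and baseline-value analyses are for the primary endpoint only, and the carried-forward analysis is tied to the primary analysis.

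**A separate SAP may settle it.** The protocol refers to a SAP for further missing-data detail, and that text is not part of the combined document. A death rule there would close the point.

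**The effect is small.** At 135 per arm and 45% response, the standard error of the difference is √(2 × 0.45 × 0.55 / 135) = 6.1 points, so +2.1 points is about a third of one standard error. This stands.

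**Two stronger readings that the documents do not support.** A reader might infer that a device causing more early deaths would be helped overall. It would not: death is a failure on the primary endpoint, mortality is reported in its own safety endpoints and adjudicated, and Early Response is tested only after primary non-inferiority and last in rank order. A reader might also infer that failed device delivery is imputed for the eTICI endpoints. Those endpoints define success as reperfusion achieved within passes of the device, so a subject with no pass has not achieved it and reads as a failure.

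**Conclusion.** The point holds, within limits. Followed literally, Section 8.2.2 gives a wrong score to subjects who die before the day-7/discharge NIHSS, and nothing in the combined document overrides it.

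The size is at most about 13 such deaths per arm of 135, with about 4 to 8 scored as responders. This rests on the 9.7% literature upper limit and an assumed response of 30-60%. Both arms' rates are inflated. The comparison is biased only if early deaths differ between arms, by about +1.4 to +2.8 points under the assumed 9.7% versus 5%. The primary endpoint is untouched. The change is worth making because the endpoint carries a superiority statement, but it concerns the last-ranked secondary endpoint.

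**What to change.** In Section 8.2.2 and in item 5 of Section 8.3.2, with matching text in the SAP, state that death before the 7-day/discharge NIHSS is an Early Response failure and is not imputed. Limit multiple imputation for this endpoint to subjects who are alive and whose NIHSS was not recorded. Settle the wording before unblinding, so that the choice cannot appear to depend on the results.

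The cost is a sentence or two in each document. No new data are needed, since deaths are already collected and adjudicated. The downside is a slightly lower Early Response rate in both arms.
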